 358 actigraph readings, and polysomnography. Globally, we hypothesize BL will improve sleep quality and
 359 quantity relative to PL, and these improvements will be associated with improvements in neurocognitive

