**FORM: Application for Human Research**

| NUMBER | FORM DATE | PAGE |
|--------|-----------|----------|
| F200 | 02/2014 | 14 of 44 |

360 function, alterations in proton metabolites in the limbic system and medial prefrontal cortex, and reduced
361 PTSD symptom severity at follow-up assessment. The following are the Specific Aims and Hypotheses:

362 **AIM 1:** Evidence suggests that morning bright light therapy suppresses daytime melatonin and
363 leads to an entrainment of the circadian rhythm that modulates daytime alertness and nighttime sleep.
364 The first objective will be to assess the validity of this effect in PTSD patients.

365 **Hypothesis 1: Six weeks of BLT will improve sleep relative to PL among PTSD subjects.**

366 **1a:** Six weeks of morning blue light therapy (BLT) will improve objective and subjective
367 measures of sleep duration and quality as measured by actigraphy, sleep logs, sleep scales, and
368 polysomnography relative to an amber light placebo therapy (PL) condition.

369 **AIM 2:** If light therapy is successful in entraining the circadian rhythm and improving nighttime
370 sleep in patients with PTSD, this should be associated with improvement in symptoms and cognitive
371 functioning, as sleep has been shown to be critical in the process of extinguishing conditioned fears.
372 Therefore, the second Aim is to evaluate the association between changes in sleep patterns and
373 improvement in symptom expression, emotional wellbeing, and cognitive functioning in patients with
374 PTSD. However, even if Aim 1 is not successful, the present study will provide important cross-sectional
375 data regarding the relationship between measured sleep, cognitive functioning, and fear extinction in
376 individuals with PTSD.

377 **Hypothesis 2: BL will improve cognitive functioning, symptoms of PTSD, and generalization of**
378 **fear extinction relative to PL.**

379 **2a:** Six weeks of BL will improve measures of neurocognitive (i.e., memory and executive
380 functions) and mood functioning relative to PL.

381 **2b:** The PTSD group receiving six weeks of BL will show significant reduction in self-
382 reported symptom scores on the PTSD symptom checklist and CAPS, lower emotional distress on clinical
383 measures, and greater *generalization of conditioned fear extinction* relative to the PTSD group receiving
384 PL.

385 **AIM 3:** At present, there are no known studies that have examined the neurobiological correlates

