386 of symptom improvement in patients with PTSD following light exposure therapy. The present study
387 aims to provide clear evidence of functional and neurochemical changes that are associated with changes
388 in sleep, cognition, and PTSD symptoms from pre- to post-treatment. Even if Aim 1 is not supported, the
389 obtained cross sectional data will provide critical insights regarding the association between sleep,
390 neurometabolites, and brain function within patients with PTSD. This correlational information is
391 currently lacking for PTSD and will fill an important knowledge gap regardless of whether the light
392 therapy is successful.

393 **Hypothesis 3: Six weeks of BL will produce reliable changes in brain activation and**
394 **neurochemistry relative to PL, particularly for PTSD subjects.**

395 **3a:** Relative to PL, six weeks of BL will lead to significantly increased ventromedial
396 prefrontal activation and reduced amygdala activation during the backward masked affect fMRI task.

397 **3b:** Relative to PL, six weeks of BL will lead to significantly greater negative functional
398 connectivity between the ventromedial prefrontal cortex and amygdala during resting state fMRI.

399 **3c:** Relative to PL, six weeks of BL will be associated with increased activation of the
400 VMPFC, and reduced activation within the amygdala and dorso-medial prefrontal cortex during the
401 extinction recall scan.

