**FORM: Application for Human Research**

| NUMBER | FORM DATE | PAGE |
|--------|-----------|----------|
| F200 | 02/2014 | 15 of 44 |

402 **3d:** Relative to PL, six weeks of BL will be associated with increased levels of GABA and
403 reduced glutamate in the amygdala-hippocampal complex and anterior cingulate gyrus as measured by
404 proton magnetic resonance spectroscopy (1H MRS).

405 **3e:** Relative to PL, six weeks of BL will produce increased levels of N-acetyl-aspartate
406 (NAA), choline (Cho), and reduced phosphocreatine (Cr) within the amygdala-hippocampal complex and
407 anterior cingulate gyrus.

408 **AIM 4:** The fourth Aim is to demonstrate whether changes in subjective and objective measures
409 of sleep are associated with changes in symptom severity, cognitive functioning, brain activation, and
410 neurochemistry. Regardless of the success of the light therapy approach outcome in Aim 1, the available
411 data will provide some of the first longitudinal data examining changes in sleep patterns over time in
412 individuals with PTSD and their correlation with these other metrics. Thus, useful data will be acquired
413 even if the primary hypothesis of Aim 1 is not supported.

414 **Hypothesis 4: Improvements in sleep noted in Hypothesis 1, will be linearly correlated with
415 improvements in cognitive and symptom functioning in Hypothesis 2 and structural and functional
416 brain changes in Hypothesis 3.**

417 **4a:** Changes in sleep parameters identified in Hypothesis 1 will correlate with
418 improvements in memory, executive functioning, and neuropsychological performance on neurocognitive
419 measures described in Hypothesis 2.

420 **4b:** Changes in sleep parameters identified in Hypothesis 1 will correlate with changes in
421 neurochemistry as outlined in Hypothesis 3d and 3e above.

423 **2) Lay Summary (approximately 400 words)**

424 Sleep disturbance is nearly ubiquitous among individuals suffering from PTSD and is a major problem
425 among service members returning from combat deployments. Recent evidence suggests that adequate
426 restorative sleep may a crucial component in the ability to generalize fear extinction learning, and
427 ultimately may be a key feature in the process of recovery from PTSD. The proposed study aims to test a
428 novel, inexpensive, and easy to use non-pharmacologic approach to improving sleep among service

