591 sleep related problems so that it may be possible to statistically control for the effect of the
592 BLT treatment on different forms of sleep problems;
593 13) Index trauma occurring before the participant is 18 years of age;
594 14) Index trauma occurring 10 years or longer prior to participation in the study;
595 15) WRAT4 reading test score indicative of less than a 6th grade level of reading comprehension;
596 16) Drug use: Marijuana use not exclusionary. Past drug dependence (other than marijuana) not
597 exclusionary if individuals have sustained remission (no drug use in the past 12 months).

598 6) Recruitment Methods and Consenting Process

599 Please note: *The Human Research Protection Office (HRPO) with US Army Medical Research and*
600 *Materiel Command must approve any major amendment to this study prior to its implementation.*
601 *Therefore, implementation of any amendment which requires HRPO approval, including use of revised*
602 *consents, will not begin until HRPO approval is received.*

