**FORM: Application for Human Research**

| NUMBER | FORM DATE | PAGE |
|--------|-----------|----------|
| F200 | 02/2014 | 31 of 44 |

1039 and gender. Randomization will consist of permuted blocks to achieve balance over time. Repeated
1040 measures analysis of variance (ANOVA) and linear mixed-model approaches will be used for the primary
1041 analyses examining the efficacy of light treatment condition on measures of mood and sleep. Between
1042 group factors will correspond to the two light conditions (BL vs PL) and will control for any baseline
1043 differences in demographic variables and severity scores as appropriate. Based on specific hypotheses,
1044 separate ANOVAs will be performed for each type of dependent variable (e.g., subjective sleep scores,
1045 CAPS-2 symptom scores, mood scores, MRS metabolites). The relationship between these change
1046 indices and sleep variables will be analyzed using correlation and linear regression models in SPSS. Tests
1047 for normality will be conducted for all variables. In the case on non-normality, appropriate data
1048 transformation or non-parametric techniques will be employed (e.g., Kruskal-Wallis or Friedman tests for
1049 ANOVA; Mann-Whitney U or Wilcoxon for 2-group comparisons). Inflation of Type I error will be
1050 controlled first through the use of planned comparisons based on the hypotheses and the use of protected
1051 omnibus F-tests. Post-hoc analyses will be undertaken with protected comparisons (e.g., Tukey) or
1052 Bonferroni adjustment. Functional MRI data will be analyzed using statistical parametric mapping
1053 (SPM8) software, implementing the general linear model to compare pre- to post-therapy changes in
1054 functional responses between the active and placebo groups and across diagnostic groups, and sleep
1055 variables will be tested as covariates in the models. Finally, proton spectroscopy data for each of the
1056 metabolites will be quantified and compared for pre- to post-therapy changes in metabolite concentrations
1057 between the active and placebo treatment groups and across diagnostic groups. Type I error during
1058 neuroimaging will be controlled via whole brain False Discovery Rate (FDR) correction or small volume
1059 corrections using Family Wise Error (FWE) rate within *a priori* specified regions of interest. To handle
1060 missing data, we will first determine the potential cause of the data loss. Statistically, missing data can be

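### The fMRI models that compare blue light with placebo may carry sleep covariates that blue light is expected to change, and the plan does not say which model supplies the arm contrast

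*Combined protocol and SAP*

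**What the plan says.** The Global Statistical Analysis Approach says that the fMRI data will be analysed with "SPM8) software, implementing the general linear model to compare pre- to post-therapy changes in" functional responses between the active and placebo groups. The same sentence ends by saying that sleep "variables will be tested as covariates in the models". It gives no timing for the sleep variables and names no primary model.

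The aims place sleep on the path from light to brain:

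- Hypothesis 1: "Six weeks of BLT will improve sleep relative to PL among PTSD subjects".
- Hypothesis 3: "Hypothesis 3: Six weeks of BL will produce reliable changes in brain activation and" neurochemistry. Hypothesis 3a reads "Relative to PL, six weeks of BL will lead to significantly increased ventromedial" prefrontal activation, with reduced amygdala activation, on the masked affect task. Hypothesis 3c makes a similar prediction for the extinction recall scan. Neither is restricted to an effect that bypasses sleep.
- Hypothesis 4: "Improvements in sleep noted in Hypothesis 1, will be linearly correlated with" improvements in cognition and symptoms and with the brain changes of Hypothesis 3.

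**The concern.** A covariate measured after randomisation and affected by treatment changes the question that the arm coefficient answers. Hypotheses 3a and 3c ask whether brain change differs between BL and PL after six weeks. With change in sleep in the model, the arm coefficient asks whether light does anything to the brain other than through sleep. If light works as the protocol expects, that coefficient shrinks because the treatment improved sleep.

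Two further costs follow. The adjusted coefficient no longer rests on randomisation alone, because unmeasured causes shared by sleep change and brain change can bias it in either direction. And with several tasks, regions and sleep measures, having adjusted and unadjusted contrasts both available, with no rule on which counts, leaves the conclusion open to choice after the results are seen.

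**Working it through.** **1. Which sleep variables are meant?** The sentence does not say, so I set it beside the places where the plan defines sleep variables for analysis.

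- The opening of D. Data Analysis turns sleep measures into change from baseline to post-treatment.
- Actigraphic Sleep Measurement averages the nightly indices over the study period. With one monitored week before treatment and six during it, a plain average over all days is 6/7 = 86% post-randomisation.
- Power Analysis pairs average sleep and change in sleep with fMRI signal change.
- The Global section limits its demographic and severity adjustment to baseline differences, but puts no such limit on sleep.

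So the variables most readily to hand are ones that Hypothesis 1 expects BL to change. The description of the fear conditioning paradigm also says that better sleep under BL is expected to improve extinction recall, which is the task behind Hypothesis 3c.

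**2. The plan's own power figures.** From Power Analysis: N = 90, 45 per arm, f = .25, α = .05.

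- Interaction: λ = f²·N·2/(1−ρ), on 1 and 88 df. The pre-post correlation ρ is not given. At ρ = 0.5, λ = 0.0625 × 90 × 2/0.5 = 22.5 and power is 0.997. At ρ = 0.3, λ = 16.07 and power is 0.978. The stated 0.99 lies between these.
- Paired test, n = 45, d = .50: 0.907, against .91 stated.
- Correlation, r = .30, N = 90: 0.839, against 0.84 stated.

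The interaction figure has no sleep covariate in it.

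**3. Effect on the change score.** For two arms of 45, λ = d²·45/2, so d = √(λ/22.5). This gives d = 1.0 at ρ = 0.5 and d = 0.845 at ρ = 0.3.

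**4. Adding a sleep covariate that treatment changes.** Let s be the BL effect on sleep in within-arm SDs (assumed) and b the within-arm slope of brain change on sleep. I take b = 0.30 from the plan's r. The remaining arm effect is d − s·b. Its standard error is √[(1−b²)·(2/45)·(1+s²/4)], on 87 df.

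Worked case, d = 0.845 and s = 0.8: the remaining effect is 0.845 − 0.24 = 0.605. The standard error is √(0.91 × 0.0444 × 1.16) = 0.217. The ratio is 2.79 and power is 0.789. The loss is 0.978 − 0.789 = 0.189.

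| | No sleep covariate | s = 0.3 | s = 0.5 | s = 0.8 |
|---|---|---|---|---|
| ρ = 0.5, d = 1.0 | 0.997 | 0.993 | 0.982 | 0.934 |
| ρ = 0.3, d = 0.845 | 0.978 | 0.957 | 0.912 | 0.789 |

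The losses run from 0.4 to 18.9 points. The plan's r = .30 is stated without regard to arm. Read as a pooled correlation, b = 0.30·√[(1+s²/4)(1+d²/4)] − s·d/4, which is below 0.30. The worst case in the table then becomes b = 0.18 and power 0.873, a loss of 10.5 points.

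**5. When the loss is larger.** Take d = 0.5 and s = 0.8, both assumed. Power without the covariate is 0.65. With it, power is 0.38, 0.21, 0.10 and 0.05 when sleep carries 25, 50, 75 and 100% of the effect. Simulation with 20,000 runs agreed: at 50% the adjusted arm coefficient averaged 0.252 with power 0.208, and at 100% it averaged −0.001 with power 0.049. At d = 1.0 and s = 1.0, power falls from 0.997 to 0.68 at 50%.

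All of these figures are for a single region's change score. They do not model the plan's small-volume-corrected test.

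**The case against.** A reader might infer that the plan has decided to judge Hypothesis 3 on a sleep-adjusted contrast. The documents do not support that.

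- Testing a covariate can mean estimating its slope, which is the Hypothesis 4 association. Where the plan means adjustment it says so: it controls for baseline differences and calls motion parameters nuisance regressors. Sleep is described in neither way.
- Power Analysis treats the arm-by-session interaction and the sleep-brain association as separate analyses. The ROI and whole-brain sections name no sleep covariate.
- Baseline sleep is available, from the week of actigraphy before Visit 2 and the Visit 2 questionnaires. If only that is meant, this bias does not arise.

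Two extensions are also tempting and should not be made. Hypothesis 3b, on resting-state connectivity, is analysed in CONN with its own covariate list, and sleep is not on it. Exclusion criterion 12a says that sleep-problem data are collected "so that it may be possible to statistically control for the effect of the" treatment on different forms of sleep problem. That is a conditional eligibility note about the mix of sleep disorders enrolled. It does not specify the fMRI models.

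All of this stands, and it limits the point to an unspecified model. It does not remove it. The covariate clause sits in the sentence that sets up the arm comparison, and no other section says that the contrast is taken without sleep.

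**Conclusion.** The point holds as a gap in specification. The plan allows sleep variables that treatment is expected to change into the fMRI models that compare the arms, and does not say which model answers Hypotheses 3a and 3c. If the contrast is read from a model with such variables, it estimates a non-sleep effect and can understate the predicted difference.

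On the plan's own f and r, the power loss is under 1 to about 19 points. That range rests on an assumed pre-post correlation of 0.3 to 0.5, an assumed sleep effect of 0.3 to 0.8 SD, and r = .30 taken as the within-arm slope. The larger losses in step 5 illustrate smaller effects or heavier mediation. The documents give no mediation share or expected sleep effect, so those losses are not predictions for this trial.

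**What to change.** In the Global Statistical Analysis Approach, replace the covariate clause with two statements:

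1. The BL-PL fMRI contrasts for Hypotheses 3a and 3c come from models with no post-randomisation sleep variable. Sleep from the baseline week or Visit 2 may be included.
2. Models with change in sleep or study-period-average sleep are run separately, with arm included. They serve only the Hypothesis 4 sleep-brain association or a mediation analysis labelled exploratory, and their arm coefficient is not read as the treatment effect.

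The cost is two sentences and one extra second-level model per task, with no new data. The downside is that any claim of an effect independent of sleep becomes exploratory.

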- All participants will be adults (age 18 to 50), thus issues regarding assent from minors are not relevant.

7) Procedures involved in the Human Research

General Procedure: Over a 4-year period, 108 participants between the ages of 18 and 50 will be recruited to participate (to reach a final n of 90 subjects, assuming 20% attrition). Participants will comprise active duty, Reserve, National Guard, or recently discharged combat-exposed military personnel or DoD contractors from Operation Enduring Freedom/Operation Iraqi Freedom (OEF/OIF) meeting DSM-V diagnostic criteria for PTSD, in addition to some non-military individuals who meet the DSM-V diagnostic criteria for PTSD. Combat-exposed individuals within 10 years of return from OIF/OEF will be eligible. An age range of 18-50 years has been selected to minimize possible developmental and degenerative effects that could be expected in younger and older subjects and to encompass the age range of the majority of military personnel.

FORM: Application for Human Research
NUMBER
FORM DATE
PAGE

F200

02/2014

23 of 44

724 Prior to data analysis, subjects who consent will have a follow-up phone call where they will be
 725 administered the PCL-5, PHQ-9, and be asked about general sleep problems using the ESS and ISI.
 726

727 The procedures will essentially be identical to those used successfully in our pilot study of patients
 728 with mTBI. Participants will attend three laboratory sessions (see Figure 10 below). Visit 1 involves
 729 informed consent, demographic data collection, and basic psychiatric assessment. Participants will be
 730 provided with a wrist actigraph sleep monitor. After a week of at home monitoring, each participant will
 731 return for Visit 2, which is involves comprehensive neurocognitive assessment, neuroimaging, fear
 732 conditioning testing, objective sleepiness monitoring and heart rate monitoring. Then participants will be
 733 randomly assigned to one of two light therapy conditions (n = 45 per group) differing only in the
 734 wavelength emitted by each light therapy device. Participants will be randomly assigned to either the BL
 735 condition or the PL condition, using computerized permuted block randomization to match groups by
 736 gender. Participants assigned to the active treatment condition will undergo 6-weeks of at-home treatment
 737 with a light device fitted with blue light (BL) diodes, while those assigned to the Placebo (PL) condition

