1061 considered as falling into three types: 1) missing completely at random, 2) missing at random, or 3)
1062 missing not at random. The type of missing data will dictate the approach. Assuming type 1, and that the
1063 number of missing values is low, we will use a standard listwise deletion procedure. However, assuming
1064 that a larger number of values is missing, and data are not missing completely at random, we will be able
1065 to apply missing data imputation methods.

1066 **Power Analysis:** A power analysis based on a proposed sample size of 90 subjects suggested that
1067 with an omnibus 2 between-groups (BL vs. PL) x 2 within-subjects (pre- vs post-treatment) mixed design,
1068 assuming a moderate effect size ($f = .25$), and $\alpha = .05$, there should provide be adequate power to detect
1069 most effects. First, the primary hypotheses of the study focus on interaction effects across groups (i.e.,
1070 treatment x session interactions), which will have exceptional power ($1-\beta = 0.99$) to detect a moderate
1071 effect size at $\alpha = .05$ (see Figure 18A). Paired comparisons within each group of will also have excellent
1072 power of .91 to detect moderate effect size changes ($d = .50$), with 2-tailed tests (see Figure 18B).
1073 Without regard to group differences, a sample size of 90 would yield power = 0.84 to detect a moderate
1074 linear association (i.e., $r \geq .30$) between a predictor variable (e.g., average sleep; change in sleep
1075 parameters, PTSD symptom severity; neurocognitive performance; etc.) and an outcome variable (e.g.,
1076 fMRI signal intensity changes; spectroscopic metabolite changes; etc.), with a two-tailed test at $\alpha = .05$
1077 (see Figure 16). Thus, the proposed sample size of $n = 45$ per group appears to provide adequate power
1078 for testing the major hypotheses of the proposed study.

FORM: Application for Human Research

| NUMBER | FORM DATE | PAGE |
|---------------|------------------|-------------|
| F200 | 02/2014 | 32 of 44 |

1079 **Functional Image Pre-Processing:** Functional neuroimaging data will be preprocessed in SPM8
1080 [123]. Following standard algorithms, functional images will be slice-time corrected, co-registered to
1081 their anatomical T1-weighted images, realigned, unwarped to correct for field inhomogeneity, normalized
1082 to the standard three-dimensional space of the Montreal Neurological Institute (MNI), spatially smoothed

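### The missing-data method is chosen after the data are seen, by classifying a mechanism that the data cannot identify; the resulting bias could run either way or be nil

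*Combined protocol and SAP*

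**What the plan says.** The missing-data text closes the Global Statistical Analysis Approach paragraph under Data Analysis. The team will first establish why data were lost, and then "The type of missing data will dictate the approach". The options are "considered as falling into three types: 1) missing completely at random, 2) missing at random, or 3") MNAR.

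Two branches follow.

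- If the data are type 1 (MCAR) and the "number of missing values is low, we will use a standard listwise deletion procedure".
- In the other branch the text supposes "that a larger number of values is missing, and data are not missing completely at random, we will be able" "to apply missing data imputation methods".

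No number defines *low* or *larger*, no imputation method is named, and no sensitivity analysis for MNAR is given.

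The same paragraph converts behavioural outcomes to change scores from baseline to post-treatment. For the primary analyses it names both repeated-measures ANOVA and linear mixed models. On expected loss, General Procedure (section 7) has 108 people "recruited to participate (to reach a final n of 90 subjects, assuming 20% attrition").

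**The concern.** A prespecified rule should lead two analysts to the same analysis. This one turns on a judgement made with the data in hand, and the data cannot settle it. A test that fails to reject MCAR in about 90 people is weak evidence for it. MAR and MNAR differ only in how missingness depends on values nobody observed.

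The protocol itself gives reasons to doubt MCAR. Staff may withdraw participants who cannot or will not comply (section 15). Those who notice discomfort from the light are told to stop using it (section 8). Payment falls with missed light days (section 12). The two devices differ in wavelength and irradiance (At Home Six-Week Light Exposure Treatment), so the reasons for leaving could differ by arm.

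If loss is related to response and differs between arms, the completers no longer represent the randomised groups, and the blue light (BL) versus placebo light (PL) comparison is biased.

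**Working it through.** **1. The rule as a table.**

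| | Judged MCAR | Judged not MCAR |
|---|---|---|
| Few values missing | Listwise deletion | No rule |
| More values missing | No rule | Imputation, method unnamed |

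Two of the four cells are empty. The boundary between rows has no number, and the data cannot establish which column applies.

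**2. The plan's own attrition figure.** 90/(1 − 0.20) = 112.5, so 113 recruits would be needed. The stated 108 is 90 × 1.20, and 18/108 = 16.7% loss. A 20% loss from 108 leaves 86.4. These people are counted from recruitment, but consent comes before the diagnostic interview and randomisation comes at the end of Visit 2. An unknown part of the 20% may therefore be lost before allocation. I use 20% per arm as an upper assumption for loss after randomisation, and 5% as an example of *low*.

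**3. Assumed mechanism.** The documents give no dropout by arm or reason, so all of the following is assumed.

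- Baseline and Visit 3 scores have SD 1 and correlation 0.5. The SD of change is √(1 + 1 − 2 × 0.5) = 1. The SD of the Visit 3 score given baseline is √(1 − 0.5²) = 0.866.
- The true BL − PL effect is 0.50 SD, with higher scores better.
- In-treatment sleep S is standard normal within arm. It has correlation r = 0.3 to 0.7 with the part of the Visit 3 score that baseline does not explain.
- In the arm with selection, the log-odds of dropout are a − S, that is, 1 per SD of poorer sleep. The other arm loses the same fraction at random.

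The bias of the listwise change-score difference is r × 0.866 × m, where m is the mean of S among those who stay. The constant a is solved so that the dropout probability averages to the stated fraction p. Then m is the mean of S × P(stay | S) divided by 1 − p. Numerical integration gives:

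- p = 0.20: a = −1.650, m = 0.173
- p = 0.05: a = −3.372, m = 0.047

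| Missing per arm | r | Bias | BL only | PL only | Same in both arms |
|---|---|---|---|---|---|
| 20% | 0.3 | 0.3 × 0.866 × 0.173 = 0.045 | 0.545 | 0.455 | 0.50 |
| 20% | 0.7 | 0.7 × 0.866 × 0.173 = 0.105 | 0.605 | 0.395 | 0.50 |
| 5% | 0.7 | 0.7 × 0.866 × 0.047 = 0.029 | 0.529 | 0.471 | 0.50 |

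The last column requires the same dropout rate as well as the same mechanism in both arms.

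**4. Does another named analysis avoid this?** I simulated 1,000,000 per arm with 20% missing and BL-only selection (Monte Carlo error about 0.002).

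| r | Listwise change score | Pre/post model adjusted for baseline | Imputation by arm from baseline and S |
|---|---|---|---|
| 0.3 | 0.544 | 0.544 | 0.500 |
| 0.5 | 0.575 | 0.575 | 0.499 |
| 0.7 | 0.608 | 0.607 | 0.503 |

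A model with only baseline and Visit 3 scores does no better than listwise deletion, because the driver of dropout is not in it. Adding in-treatment sleep removes the bias.

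**5. What 0.105 SD means for the test.** With 45 per group the standard error is √(2/45) = 0.211, and 0.105/0.211 = 0.498. With no true effect, the two-sided rejection rate is 1 − Φ(1.960 − 0.498) + Φ(−1.960 − 0.498) = 0.072 + 0.007, or about 8% instead of 5%.

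**The case against.** A reader might infer that the plan will use listwise deletion at 20% attrition and so inflate the BL effect. The documents do not support that reading, for four reasons.

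- **Listwise deletion is conditional.** It requires both MCAR and few missing values, and under true MCAR it is unbiased. The text directs a larger loss that is not MCAR towards imputation. A 20% loss linked to in-treatment sleep belongs in that branch if it is classified correctly.
- **The 20% is not shown to be loss after randomisation.** Exclusions at intake and losses in the baseline week come before allocation and cannot bias the comparison.
- **Nothing fixes the direction.** Inflation needs selection that is stronger in BL. The mirror case in PL shrinks the estimate, and equal selection leaves it unchanged.
- **Some outcomes do not need Visit 3.** Actigraphy and diary sleep are recorded daily at home. Linear mixed models are also named, and fitted to all available data they are valid under MAR.

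All four points stand, and they limit the concern to a flawed and incomplete rule. They do not remove it. Correct classification is exactly what the data cannot guarantee, and the undefined threshold leaves room to call a material loss *low*. Repeated-measures ANOVA is named beside the mixed model with no choice between them, and it and the change scores need Visit 3 for the clinic-based outcomes. A pre/post mixed model without in-treatment data assumes that dropout is explained by baseline and arm alone (step 4).

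**Conclusion.** The concern holds in this form: the plan selects its missing-data method after the data are seen, on a classification that cannot be verified. It gives no threshold, leaves two of four cases without a rule, names no imputation method and has no MNAR analysis. Listwise deletion could therefore be used where its assumption fails.

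Under the assumed mechanism, a true 0.50 SD effect would be estimated at about 0.40 to 0.61 SD with 20% missing per arm and selection in one arm. With 5% missing the range is about 0.47 to 0.53. With identical selection in both arms there is no bias. These figures rest on an assumed dropout slope of 1, correlations of 0.3 to 0.7, and 20% as an upper assumption. They show what is possible and do not predict this trial. Even the largest bias, 0.105 SD, is about half the standard error of 0.211. The matter should be settled before analysis begins, but it does not undermine the design.

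**What to change.** Replace the rule with one primary method, fixed in advance and applied whatever the pattern of loss:

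1. Include every randomised participant, in the assigned arm.
2. Use a method valid under MAR that draws on weekly actigraphy, diary sleep and light-use adherence. Multiple imputation, for example by arm with baseline outcome and these weekly data as predictors, would serve. So would a joint mixed model that includes the weekly data. Either is acceptable, but one should be named.
3. Report the complete-case analysis as secondary.
4. Add one delta-shift analysis for MNAR: worsen the imputed values in one arm by a stated amount and report how the estimate moves. The movement is the missing fraction times delta, so at 20% missing a delta of 0.25 SD in BL moves the estimate by 0.20 × 0.25 = 0.05 SD.
5. State how many of the expected losses fall before and after randomisation.

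The cost is revised analysis wording and modest extra programming, with no new data. One practical limit should be recorded: actigraphy and light-use records for a participant who withdraws depend on the equipment being returned, whereas the diary is kept online.
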